The primary purpose of this protocol is to understand the role of physical activity on BAT mass and circulating batokines, and how these variables relate to cardiac and physical function in older adults. A formal sample size calculation was not performed. Rather, we referred to published studies with similar experimental designs (determination of BAT mass by PET scan) as a guide for sample size determination. From the published literature we determine that an n=15 per group (active and sedentary) will provide sufficient statistical power to detect differences in BAT mass.

Statistical Analysis Plan

The analysis will involve multiple steps and draw on statistical methods ranging from simple descriptive statistics to the modeling of repeated measures outcome data accounting for potential missing observations. The major outcomes of the study, the BAT mass, circulating batokines, muscle mass, strength, power and quality, and VO₂max will be compared using an unpaired student t-test to explore baseline differences between older athletes and older sedentary groups. Additionally, repeated measures ANOVA will be performed on the dependent variables as a function of the exercise intervention in the older sedentary group. Multiple linear regression will be used to determine how BAT mass and circulating batokines explain variation in physical characteristics of muscle (strength, quality) and cardiovascular health (VO₂max). Sex will be explored as a biological variable.

Potential Risks and Benefits

Potential Benefits

Participants will likely receive no direct benefit from taking part in this research study.

Potential Risks

RMR/RQ. There is no physical risk associated with RMR/RQ. Other risks include a feeling of claustrophobia experienced by some participants while under the transparent “hood”.

Protection Against Risk:

- A member of the study staff will remain with the subject at all times to ensure his/her comfort.

Blood draws and Intravenous lines (lab samples and infusions, e.g.). There is a risk of pain, vasovagal syncope, hematomas, and/or infection at the blood draw site (low risk of serious AEs). The total volume of blood drawn is over the course of the study is approximately 372 mls.

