DEXA scan. There is a very small risk of cancer with excessive exposure to any radiation. There are also risks for unborn children associated with radiation exposure. The radiation dose from the scan is less than a chest x-ray, or less than half the average amount a person would receive in a day in America.

Maximal Oxygen Consumption (VO_{2max}). There is a risk of changes to blood pressure, irregular, fast or slow heart rhythm, fainting, and in rare instances (<0.01%) heart attack, stroke, or death with exercise testing, at similar rates to exercising during daily life.

Activity/Heart Rate Monitoring. There are no risks associated with the wearing of activity monitors. However, the Bodymedia armband has sensor pads that touch the skin that may be irritating for some participants. Participants with nickel allergies will not be required to wear the Bodymedia activity monitor.

Biodesx/Strength testing/Exercise/Maximal Oxygen Consumption (VO_{2max}). There is a risk of changes to blood pressure, irregular, fast or slow heart rhythm, fainting, and in rare instances (<0.01%) heart attack, stroke, or death with exercise testing, at similar rates to exercising during daily life.

Magnetic Resonance Imaging and Spectroscopy. There are no known biological risks associated with magnetic resonance imaging and spectroscopy. Some short-term discomfort may be experienced. The short-term risks associated with MRI are minimal, but include heating, loud noises and claustrophobia. There are some people who should not undergo MRI; the contraindication is largely based on the presence of metal objects within a person (i.e. pacemaker, aneurysm clip, metal fragments, etc.).

Cardiac Function - Echocardiogram A transthoracic echocardiogram carries no risk. There's a chance for slight discomfort when the electrodes are removed from the skin. This may feel similar to pulling off a Band-Aid.

Hyperinsulinemic-euglycemic clamp. There is a risk of hypoglycemia (low blood sugar) during the clamp.

Mitigation of Risks

Blood draws and Intravenous lines (lab samples and **infusions, e.g.**). All venipuncture will be conducted by qualified staff using aseptic techniques.

DEXA scan. A urine pregnancy test will be done prior to scans of all women of childbearing potential (all women except those with prior hysterectomy, tubal ligation, or absence of menses for ≥ 2 years).

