Participant Request for Withdrawal from Study

Participation in this study is voluntary. Participants may decide not to participate in this study or may withdraw from this study at any time without penalty or loss of benefits.

Data Collection and Follow-up for Withdrawn Participants

Participants who request withdrawal or who are withdrawn by the PI from the study will have their data maintained in the research database. This data and biospecimens from the

withdrawn participant may be included in subsequent analysis. Participant withdrawal of biospecimens is not an option.

Adverse Event Reporting

Adverse Events

An adverse event (AE) is defined as both an expected side effect that is of a serious nature, or an unexpected side effect/event regardless of severity. Each participant is evaluated for adverse events at every study visit. Any event that is reported to the study staff and which meets the criteria of an adverse event will be documented as such and graded as to its attribution (unrelated to protocol, or possibly, probably, or definitely related to protocol) and severity (mild, moderate, or severe).

Recording of Adverse Events

At each contact with the participant, the investigator will seek information on adverse events by specific questioning and, as appropriate, by examination. Information on all adverse events will be recorded immediately in the source document, and also in the appropriate adverse event module of the case report form (CRF). All clearly related signs, symptoms, and abnormal diagnostic procedures results will be recorded in the source document.

Notification of Adverse Events

Adverse events will be reported according to AdventHealth Orlando IRB guidelines.

Safety Monitoring Plan

Safety Monitoring

Research and safety data will be reviewed by the PI. This review will take place at regular meetings with the clinical coordinator and medical investigator where the safety labs for each new participant will be reviewed. Other items discussed will include: progress or adverse events occurring in the following: participant confidentiality, participant recruitment, and consent process. All will monitor response to tolerance of and effectiveness of the exercise program.

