Progress reports, including patient recruitment, retention/attrition, and AEs from the reviews will be compiled into an annual report and will include a list and summarization of adverse events. In addition, the annual report will address (1) whether adverse event rates are consistent with pre-study assumptions; (2) reason for dropouts from the study; (3) whether all participants met entry criteria; (4) whether continuation of the study is justified on the basis that additional data are needed to accomplish the stated aims of the study; and (5) conditions whereby the study might be terminated prematurely.

Data and Safety Monitoring Board (DSMB) or Equivalent

N/A

Ethical Considerations

Participation in this study is voluntary. Participants may decide not to participate in this study or may withdraw from this study at any time without penalty or loss of benefits. No vulnerable populations will be studied in this protocol.

Sharing of Results with Participants

Participants will be offered the opportunity to meet with the PI to review the results of their outcomes. Copies of their testing results will be made available to the participants. In addition, the PI will provide an overview of the study's outcome to the participant if he or she requests the information.

Funding Source

This study will be supported by a sub award from a prime award from the National Institutes of Health, National Institute of Aging (R01 AG060542), P.I., [name]. Sub Award PI and Co-Investigator, [name]. The IRBNet # for this grant is 1456947.

Participant Stipends or Payments

Participants will receive a total of \$1425.00 (or up to \$1641 with exercise extension visits) if in the OS group, and \$500.00 if in the OA group, upon the completion of all study visits. Ride shared services, for example Uber Health or Lyft, may be made available to the participants by the study team with PI approval. Travel services will be arranged only by the study team with approval. If participant is unable to complete all study visits, the stipends will be prorated to the following:

Athlete Group Total Payment: \$500	Phase 1	SV1	\$0
V1		\$75	
V2		\$75	
V3		\$350	

Sedentary Group Total Payment: \$1425 (up to \$1641 with Extension Visits)	Phase 1	SV1	\$0
		V1	\$75
		V2	\$75
		V3	\$150
	Phase II	V4, 5, 6, 7	
		V8, 9, 10, 11	
		V12, 13, 14, 15	
		V16, 17, 18, 19	
		V20, 21, 22, 23	
		V24, 25, 26, 27	
		V28, 29, 30, 31	
		V32, 33, 34, 35	
		Exercise Extension	
		V36	\$75

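### The adverse event definition excludes expected non-serious events, so the AE module, the annual AE list and the AE rate reviewed each year omit that class

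*Combined protocol and SAP*

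**What the plan says.** Under Adverse Event Reporting, the Adverse Events section says that an AE is "defined as both an expected side effect that is of a serious nature, or an unexpected side effect/event regardless of severity". It then makes that definition the condition for recording: "Any event that is reported to the study staff and which meets the criteria of an adverse event will be documented as such", after which the event is graded for attribution and for severity (mild, moderate or severe).

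Recording of Adverse Events sends information on AEs to the source document and also places it "in the appropriate adverse event module of the case report form (CRF"). A further sentence reads "All clearly related signs, symptoms, and abnormal diagnostic procedures results will be recorded in the source document".

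Potential Risks names the foreseeable harms. For blood draws and intravenous lines: "There is a risk of pain, vasovagal syncope, hematomas, and/or infection at the blood draw site (low risk of serious AEs"). For the glucose clamp: "There is a risk of hypoglycemia (low blood sugar) during the clamp". For exercise and strength testing it names blood pressure changes, abnormal heart rhythm and fainting, and, in rare instances, heart attack, stroke or death.

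Safety Monitoring provides for an annual report, which "will include a list and summarization of adverse events". Item (1) of that report is "whether adverse event rates are consistent with pre-study assumptions".

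**The concern.** An AE definition normally sets what is collected, while seriousness and expectedness set what is reported onward and how fast. Here the two functions are merged: expectedness and seriousness decide whether an event is an AE at all. The harms that the protocol itself foresees are the ones most exposed to this filter, because an event that was foreseen has to be serious to pass it.

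What is at stake is the completeness of the harms record in adults aged 65 to 90. An older sedentary (OS) participant has up to two clamps, two maximal exercise tests and at least 32 training sessions. The trial has no data and safety monitoring board, and the annual report is the one place where the protocol says AE rates are compared with anything.

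**Working it through.** The documents give no AE count or rate for these harms, so there is no figure to reproduce. The check is a reading of the definition followed by a trace through the recording and reporting text.

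**Step 1. The definition as a two-by-two table.**

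| | Serious | Non-serious |
|---|---|---|
| Expected | AE | not an AE |
| Unexpected | AE | AE |

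The grammar of the definition is faulty, since it joins two alternatives with both a *both* and an *or*. No reading of it fills the empty cell.

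**Step 2. Does severity grading fill the cell?** No. Grading applies to events that have already met the definition. The excluded class is also not defined by grade: a severe but non-serious expected event is left out, and a moderate event that is serious is kept.

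**Step 3. What falls in the cell?** The protocol labels no event as expected and does not define serious. Taking the Potential Risks list as the expected set is an inference, but a natural one. Non-serious hypoglycemia, vasovagal syncope, hematoma, fainting and blood pressure change then fall in the cell. The blood-draw entry itself describes the risk of serious AEs as low, so most such events would be expected to be non-serious. Under Muscle Power Testing, blood pressure that stays high after the test ends the visit and is notified to the PI and Medical PI. Because blood pressure change is a listed risk, that event could still fall outside the AE definition if judged non-serious.

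**Step 4. Does any other text bring the class back?**

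- The sentence on related signs and symptoms reaches the source document. It does not mention the AE module or the annual list.
- Data De-identification has source data transcribed into the electronic CRF. That may carry a symptom into the database, but not as an AE.
- Notification of Adverse Events refers to IRB guidelines for reporting. It imports no other definition.
- Safety Monitoring builds its list and its rate on AEs, and so on events that passed the definition.

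The class therefore stays out of the numerator of the item (1) rate.

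**Step 5. Illustration of scale, under assumed rates.** Inputs: 15 completers or 18 enrolled per group (Participants Recruitment and Screening). There is one clamp per older athlete (OA), and two per OS participant because Phase III testing is described for the OS group.

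- Clamps, completers: 15 × 1 + 15 × 2 = 45
- Clamps, all enrolled completing: 18 × 1 + 18 × 2 = 54
- Expected events = clamps × p
- P(at least one) = 1 − (1 − p)^clamps

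Here p is the chance of a non-serious hypoglycemia per clamp. The documents do not give p, and the values below are assumptions. The probability treats clamps as independent.

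| Assumed p | Events in 45 clamps | P(≥1), 45 | Events in 54 clamps | P(≥1), 54 |
|---|---|---|---|---|
| 1% | 0.45 | 0.364 | 0.54 | 0.419 |
| 5% | 2.25 | 0.901 | 2.7 | 0.937 |
| 10% | 4.5 | 0.991 | 5.4 | 0.997 |

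The current definition would list none of these events as AEs if they are classed as expected and non-serious.

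**The case against.** Several points on the other side are sound, and they limit what can be claimed.

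- **The events may not be lost.** Related signs and symptoms go to source documents, and source data are transcribed. Plasma glucose is measured every 5 to 10 minutes during the clamp, blood pressure is taken before and after power testing, and heart rate, blood pressure and ECG are recorded throughout the maximal test. This stands: many cases could be reconstructed. They would still lack an AE label, an attribution and a grade.
- **Classification is left to judgement.** With neither expected nor serious defined, staff could record some of these events as AEs. This stands as a limit on certainty, but it also means that the count would depend on who classifies.
- **The annual comparison may be like with like.** If the pre-study assumptions use the same definition, item (1) is internally consistent. The documents neither show this nor rule it out. The only numeric harm rate given is below 0.01%, for heart attack, stroke or death with exercise testing. Even a like-with-like comparison would say nothing about the omitted class.
- **No planned analysis is affected.** AEs are not among the listed outcome measures. This stands.

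A reader might also infer that safety oversight consists only of the PI's meetings and the annual report. It does not: Resources Available names a medical oversight team, a Medical Oversight Committee and a Quality Committee with a role in AEs, and the medical investigator attends the review meetings. Nor do the documents tie continuation to the AE rate. Item (4) of the annual report asks whether further data are needed for the study's aims, and only item (1) uses AE rates.

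**Conclusion.** The point holds and is wrong as written. It is a stated rule with a poor result, not a missing detail. If the text is followed, expected non-serious events of any severity grade do not enter the AE module or the annual AE list, and the item (1) rate leaves them out.

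The conclusion rests on one inference: that the harms listed under Potential Risks count as expected.

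Three stronger readings are not supported. It is not true that hypoglycemia, syncope or hematoma go uncounted altogether, since serious cases meet the definition. The gap cannot be expressed as a percentage undercount of AEs, because the share of events in the excluded class is unknown. Nor do the documents show that the omitted events are the most frequent harms. The 0.45 to 5.4 clamp events shown above indicate scale under assumed rates and are not estimates for this trial.

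The definition should be corrected, but the defect does not undermine the outcome analyses.

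**What to change.** Define an AE as any untoward medical occurrence after consent, regardless of expectedness, relatedness or severity. Record every such event in the CRF AE module, with seriousness and expectedness as separate fields alongside the existing attribution and severity grades. Define both terms, and say whether the Potential Risks list is the reference for expectedness. Use the two fields only to decide IRB notification under the IRB guidelines. State the pre-study rates that the annual report will use for item (1), on the same definition.

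The cost is a protocol wording change, two CRF fields and some extra entries. Whether IRB notification stays the same cannot be judged from the documents, because the guidelines are not reproduced. The notification wording must be checked against them before the change is made.

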Appendix: Schedule of Activities

	Phase I: Pre-Intervention					Phase II: Intervention								Phase III: Post-Intervention					
	Screening	Baseline				V 4-7	V 8-11	V 12-15	V 16-19	V 20-23	V 24-27	V 28-31	V 32-35	Exercise Extension (prn)	V 36	V 37	V 38	V 39	
Visit	SV1	V1	V2	V3		D 0* - D 3	D 7 - D 10	D 14 - D 17	D 21 - D 24	D 28 - D 31	D 35 - D 38	D 42 - D 45	D 49 - D 52		D 56	D 60	D 64	D 70	D 71
Day	D -54	D -26	D -19	D -7	D -6														
Windows **	within 28 days of V1+2d	±2	±2	±4		CRU overnight	Wk 1	Wk 2	Wk 3	Wk 4	Wk 5	Wk 6	Wk 7	Wk 8	*Wk 9-11	+3	±2	±3	±2
OA Group	X	X	X	X	X	X/EOS	X	X	X	X	X	X	X	X		X	X	X	X/EOS
OS Group	X	X	X	X	X	X	X	X	X	X	X	X	X	X		X	X	X	X
Informed Consent	X																		
Inclusion/Exclusion Criteria	X																		
Demographics	X																		
Past Medical History	X																		
Concomitant Medication/Supplements	X	X	X	X	X	X	X	X	X	X	X	X	X	X	X	X	X	X	X
Physical Examination	X															X			
Adverse Events	X	X	X	X	X	X	X	X	X	X	X	X	X	X	X	X	X	X	X
Height	X			X													X		
Weight (metabolic)	X	X	X	X	X	X										X	X	X	X
BMI	X															X			
Waist circumference	X															X			
Vital Signs (BP, Pulse, Respiration, Temp)	X	X	X		X											X	X	X	X
ECG (12-lead)	X															X			
Study Specific Questionnaires:																			
MMSE, PASE, CHAMPS, Exercise History	X																		
Blood Collection: Lipid Panel, CMP, CBC with differential, TSH, HbA1c	X															X			
Blood Collection: EDTA Plasma (for		X															X		
Covid testing	X*		X*													X*		X*	
Urine Collection	X																		
Handgrip strength	X															X			
SPPB	X															X			
Step Test	X															X			
Dispense 3 Day Food Diary	X																X		
Collect 3 Day Food Diary			X														X		
MRI	X																X		
DEXA	X															X			
VO2max test/stress test	X															X			
Placement of Accelerometers	X																X		
Collect Accelerometers		X*	or X													X*	or X		
Echocardiogram		X														X			
1-RM Muscle Strength	X															X			
Biodex	X															X			
Blood Collection: POC Glucose (clamp prep)			X														X		
Dinner Meal Consumption			X														X		
24-hr Urine Collection					X													X	
Hyperinsulinemic-Euglycemic Clamp					X													X	
RMR/RQ					X														X

